- Patients to be female, aged 18-45 years
- Without previous dilatation and curettage
- Undergoing dilatation and curettage for the current delayed miscarriage
- All participants should be with normal liver/renal function and without systemic disease
- Agree to use adequate forms of contraception throughout the study
- Be in good compliance with the follow-up examination according to the study protocol

The exclusion criteria:

- Known/suspected intolerance or hypersensitivity to hyaluronan or its derivatives
- Genital tract malformation
- Inflammation of genital tract or pelvic cavity, clinical evidence of cancer in genital tract
- Suspected genital tuberculosis
- Abnormal blood coagulation
- Medical histories of peripheral vascular disease, alcohol/drug abuse, and mental illness
- Acute or severe infection
- Autoimmune diseases.

Trial Process Flow

Trail processes	Recruitment and Treatment		Follow-up
	Two weeks before surgery	Surgery	Three months after surgery (± 7 day)
Window period	X		
Informed consent form	X		
Inclusion/exclusion criteria	X		
Dropout criteria			X
General data	X		
Physical exam on vital signs	X		
Medical history	X		
Surgical history	X		
Diagnosis	X		
Surgery evaluation		X	
Medication		X	
AFS adhesion evaluation	X		X
Clinical symptoms and vital signs	X	X	X
AE		X	X
Randomization		X	
Device application		X	

Randomization and Interventions:

The participants were randomly assigned into group of either D&C alone (control group) or D&C plus intrauterine MateRegen[®] gel application (treatment group) in a 1:1 ratio; and the random sequences were generated by SAS[®] 9.13 (center stratified blocked randomization, block=10) (SAS Institute, Cary NC).

Surgical Procedure and Gel Application

All D&C procedures were performed by suction curettage under general anesthesia in accordance with procedural standards. At the end of the D&C procedure a syringe of MateRegen[®] gel (3ml) was applied to the uterine cavity for patients assigned to the treatment group through a 15-cm sterile delivery cannula, whereas nothing was applied to the uterine cavity for patients in the control group.

Follow-up and Measurement:

A follow-up hysteroscopic examination was scheduled 3 months (± 7 days) after the D&C procedure at about one week after the clean of menstrual bleeding. A pregnancy test was performed and before hysteroscopic examination. For patients with positive pregnancy test, the hysteroscopic examination was canceled.

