Findings at follow-up hysteroscopy were evaluated and recorded according to the American Fertility Society (AFS) classification.

Table. The American Fertility Society (AFS) classification of intrauterine adhesion (1988)#

Extent of cavity involved	<1/3	1/3-2/3	>2/3
Score	1	2	4
Type of adhesions	Filmy	Filmy & dense	Dense
Score	1	2	4
Menstrual pattern	Normal	Hypomenorrhea	Amenorrhea
Score	0	2	4
Prognostic classification			
Disease severity	Cumulative score		
Stage I (mild)	1-4		
Stage II (moderate)	5-8		
Stage III (severe)	9-12		

#

Endpoints:

The primary endpoint was the number of women with formation of IUAs. The secondary endpoints included the adhesion scores of extent of uterine cavity involved, type of adhesion and menstrual pattern, the cumulative adhesion score and the severity of IUAs graded according to AFS classification. The safety was monitored based on the complications and adverse events recorded that was possibly related to the MateRegen[®] gel application.

Participant number

The primary hypothesis of this trial was to demonstrate the superiority of D&C plus MateRegen[®] gel over the D&C alone, with respect to the incidence of IUAs. The primary assumption was that the estimated incidence was 30% in control group and would be reduced to 15% by application of MateRegen[®] gel. With a 2-tailed 0.05 significance level and 20% loss rate during follow-up, 300 patients with 1:1 allocation would yield 80% power to detect the superiority.

Statistical analysis Plan

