All randomized women who started treatment were included in analysis according to the intent-to-treat (ITT) principle. Continuous variables were expressed as mean \pm standard deviation (SD) or median \pm quartile range (QR). Categorical variables were described by counts and percentages. The student's t-test/Wilcoxon rank-sum non-parametric test and chi-square test/Fisher's exact test were used to check the homogeneity of baseline characteristics. The Wilcoxon rank-sum non-parametric test was used if variables do not follow the normal distribution and the results were expressed as median (Quartile Range) (QR). The Cochran-Mantel-Haenszel (CMH) Chi-Square test with center effect adjustment was performed to estimate the incidence difference between groups. The analysis of covariance with center effect adjustment was performed to estimate the difference of intrauterine adhesion scores between groups. All analyses were performed by using SAS[®] 9.13 (SAS Institute, Cary NC), and a $p \leq 0.05$ (two-tailed, $\alpha = 0.05$) was considered to be statistically significant.

#

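### Does the general Wilcoxon/median sentence conflict with the centre-adjusted ANCOVA named for the adhesion scores?

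*Combined protocol and SAP*

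**What the plan says.** The Statistical analysis Plan section is one paragraph. In order, it gives:

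- summaries for continuous variables, either mean with SD or median with quartile range, not tied to any endpoint;
- t-test or Wilcoxon, and chi-square or Fisher, for comparing baseline characteristics;
- the sentence at issue: "The Wilcoxon rank-sum non-parametric test was used if variables do not follow the normal distribution and the results were expressed as median", followed by the quartile range;
- a centre-adjusted CMH test for incidence;
- the rule for the scores: "The analysis of covariance with center effect adjustment was performed to estimate the difference of intrauterine adhesion scores between groups".

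The analysis set is wide: "All randomized women who started treatment were included in analysis according to the intent-to-treat (ITT) principle". Women without adhesions therefore belong in the comparison.

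Under Endpoints, the secondary outcomes are the three AFS item scores, "the cumulative adhesion score and the severity of IUAs graded according to AFS classification". Randomization and Interventions describes "center stratified blocked randomization, block=10". Participant number assumes that "the estimated incidence was 30% in control group and would be reduced to 15% by application of MateRegen".

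**The concern.** The Wilcoxon sentence speaks of variables in general. Read literally, it reaches the adhesion scores, which will not be normal if most women score 0. There would then be two rules for one outcome: ANCOVA with centre, or Wilcoxon without centre and a median summary. The plan does not say which takes precedence or how normality is judged.

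Three consequences would be at stake:

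- The p-value for a secondary score could depend on which sentence the analyst followed, and either could be presented as the planned one.
- Medians of 0 in both arms would hide a halving of incidence.
- The ordered severity grade has no clearly named test. If Wilcoxon were used for it, centre would be ignored although randomisation is stratified by centre.

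**Working it through.** **The plan's own figure.** With 30% v 15%, two-sided 0.05, 80% power and a pooled proportion of 0.225:

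n per arm = [1.960·√(2·0.225·0.775) + 0.842·√(0.30·0.70 + 0.15·0.85)]² / 0.15² = 120.5, so 121. Dividing by 0.8 for loss gives 152 per arm, 304 in total, against 300 stated. With 120 examined per arm, power is 79.8%. The sample size reproduces and does not depend on this point.

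**Share of zeros.** 300 × 0.8 = 240 examined, 120 per arm. Women without adhesions: 120 × 0.70 = 84 control and 120 × 0.85 = 102 gel, so 186/240 = 77.5%. This applies to extent and type if a clean cavity scores 0. The AFS table prints no 0 for those two items, but the wide analysis set points to that reading. In simulation, normality was rejected every time.

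**Medians and quartiles, clean cavity = 0.**

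- A non-zero control median needs at least 60 of 120 women with adhesions. At 30% the probability is 3.5 × 10⁻⁶, so both medians are 0.
- The plan pairs the median with the quartile range. The control upper quartile is above 0 if at least 30 of 120 have adhesions: probability 1 − 0.096 = 0.904. The gel upper quartile is 0 if fewer than 30 do: probability 0.997. The product is about 0.90, so the planned summary would usually show a difference.

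**Cumulative score if adhesion-free women keep menstrual points.** If a share m of them have a menstrual change, the zero share is 0.70(1 − m) in control and 0.85(1 − m) on gel. At m = 20% the control non-zero share is 1 − 0.56 = 44%, and the chance of a non-zero control median rises to 0.11. The expected control median leaves 0 at about m = 29%, the gel median at about 41%.

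**Does the choice of test matter?** Simulation of the cumulative score: 6 centres × 20 women per arm, 3000 replicates, linear model with centre and arm v rank-sum without centre. The documents give no severity distribution, so three were assumed for women with adhesions. Shares at extent and type 1/2/4, then menses 0/2/4: mild 60/30/10% and 70/25/5%; moderate 40/40/20% and 50/35/15%; severe 25/40/35% and 40/35/25%. Items were drawn independently within a woman.

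| Scenario | ANCOVA power | Wilcoxon power | Tests disagree |
|---|---|---|---|
| Only incidence falls, clean = 0 (mild, moderate, severe) | 70.9, 74.0, 73.4% | 79.1, 80.0, 78.1% | 10.4, 8.0, 6.8% |
| Severity also falls, clean = 0 (moderate to mild, severe to moderate) | 94.9, 91.9% | 88.1, 85.7% | 6.9, 6.8% |
| Only incidence falls, menstrual points kept at 20% | 61.2, 67.1, 70.9% | 59.7, 63.0, 64.7% | 11.0, 11.6, 12.9% |
| Severity also falls, menstrual points kept at 20% | 92.2, 90.0% | 74.5, 71.3% | 18.0, 18.9% |

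Independence of the items matters. If they move together fully, clean cavity = 0 and only incidence falls, a t-test standing in for ANCOVA has 58–66% power against about 80% for Wilcoxon, a gap of about 14 to 22 points, and disagreement is 17–25%.

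**Type I error.** With 15, 22.5 or 30% incidence in both arms: ANCOVA 4.2–5.6%, Wilcoxon 4.3–5.7%, whichever is significant 5.8–7.0%.

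**Severity grade.** If only incidence falls, a centre-stratified CMH row-mean-scores test with integer scores had 73% power against 78% for unadjusted Wilcoxon. Moving to that centre-adjusted test is not a clear gain.

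**The case for a change.** The strongest argument for a change is that the preceding sentence already names Wilcoxon for baseline, so a baseline-only reading makes the disputed sentence largely redundant, whereas a general reading gives it a purpose. Non-normality of extent and type is certain if clean cavities score 0, the tests do disagree in a noticeable share of trials, and a few words would settle it. The gap for the grade also remains on either reading.

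Part of this stands: the wording is loose and the grade has no explicit test. But the sentence is not idle on the baseline reading. The sentence before it offers the t-test and Wilcoxon as alternatives, and this one says when the second is used and how it is reported. The score sentence names its outcome, and specific text governs general text. For the grade, the centre-adjusted CMH test already named for incidence is as much a candidate as Wilcoxon; a CMH test with rank scores would respect the stratification and keep the power of Wilcoxon. An analyst can reach that without an amendment.

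**Conclusion.** This is an ambiguity of wording, not a conflict, and no change to the plan follows. ANCOVA with centre is the named method for the scores. Insisting on it merely restates the plan; replacing it would take a side in a trade-off whose direction depends on unknowns. Wilcoxon gains about 5 to 8 points when only incidence falls, clean cavities score 0 and the items are independent, and more if the items move together. ANCOVA gains when severity also falls, and under independent items it is also ahead when menstrual points are kept at 20%.

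Disagreement in roughly 7–25% of trials is real, but it arises between two valid tests of a secondary outcome, each with about 5% type I error. Zero medians would not hide the effect: upper quartiles would differ in about 90% of trials with clean cavity = 0, mean and SD are also allowed, and incidence is reported in its own right.

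The power and disagreement figures rest on assumed severity distributions and menstrual rates. The conclusion does not: it rests on the order of the sentences and on both tests being valid. The primary endpoint, its CMH test and the sample size are unaffected.

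### Five overlapping AFS secondary endpoints share an unadjusted two-sided 0.05 threshold, and nothing in the SAP ties a secondary claim to success on the primary

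*Combined protocol and SAP*

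**What the plan says.** The Endpoints section names one primary: "The primary endpoint was the number of women with formation of IUAs". The secondaries are the "adhesion scores of extent of uterine cavity involved, type of adhesion and menstrual pattern, the cumulative adhesion score and the severity of IUAs", graded by AFS. That makes five. The AFS table shows how they are linked: the cumulative score adds the three item scores, and Stages I to III are bands of that cumulative score.

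The Participant number section frames one primary hypothesis, superiority on IUA incidence, and sizes the trial on it alone.

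The Statistical analysis Plan gives the incidence test as follows: "The Cochran-Mantel-Haenszel (CMH) Chi-Square test with center effect adjustment was performed to estimate the incidence difference between groups". The adhesion scores are compared by centre-adjusted analysis of covariance. No test is named specifically for stage. The closing sentence, which speaks for all the analyses, says that a two-tailed p at or below 0.05 "was considered to be statistically significant".

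The documents contain no testing order, key secondary, multiplicity adjustment or condition on the primary result. They do not say that the secondaries are exploratory.

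**The concern.** Because the threshold covers all analyses, the plan as written lets any of the five AFS results be called significant after the only primary endpoint has failed. All five are efficacy measures, and the study objective is efficacy against adhesion formation. Such a result could therefore be read as support for the device when the sized comparison did not show it.

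The overlap adds to the problem. The sum and the stage are functions of the three items. Extent and type are also closely tied to whether a woman has an adhesion at all. Several small p-values may look like independent confirmation when they are largely one signal.

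The planned power is 80%, so the primary would miss about one time in five even if the assumed effect were true. The plan should say beforehand what secondary p-values mean in that event.

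**Working it through.** **1. The plan's own figure.** The inputs from Participant number are "the estimated incidence was 30% in control group and would be reduced to 15% by application" and "With a 2-tailed 0.05 significance level and 20% loss rate during follow-up". The usual two-proportion formula, pooled and without continuity correction, has mean rate (0.30 + 0.15)/2 = 0.225:

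n per arm = [1.960·√(2·0.225·0.775) + 0.842·√(0.30·0.70 + 0.15·0.85)]² / 0.15² = (1.157 + 0.489)² / 0.0225 ≈ 120.5, so 121.

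Total 242; 242/0.80 = 302.5, so 303. The plan says "300 patients with 1:1 allocation would yield 80% power to detect the superiority". In reverse, 300 × 0.80 = 240 evaluable women, 120 per arm, gives power 0.798. The stated size is reproduced to within about 1%. It concerns the primary only; the documents state no family-wise error rate.

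**2. Upper reference.** If the tests were independent, the chance of at least one p ≤ 0.05 under no effect would be 1 − 0.95⁵ = 22.6% for five tests and 1 − 0.95⁶ = 26.5% for six. This is too high here because the endpoints share items.

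**3. Simulation with the overlap built in.** From the documents: 240 evaluable women, 1:1 allocation, six centres, AFS item scores and stage bands, centre-stratified CMH for incidence, and centre-adjusted ANCOVA for the four scores. Assumed, because the documents are silent:
- equal centres;
- IUA incidence 15-30% in both arms;
- a range of item distributions from mild to severe;
- inter-item correlation 0 to 0.9;
- the menstrual item scored either in all women or only in those with IUA;
- stage tested by a stratified mean-score CMH or a 3-df chi-square.

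Each scenario used 10,000 trials with no gel effect. Near 12% the simulation error is √(0.12·0.88/10,000) ≈ 0.3 percentage points.

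One scenario as an example (30% incidence, uncorrelated items, menstrual item scored only with IUA, mean-score stage test):
- primary error 4.6%; the five secondaries 4.6-5.2% each;
- at least one of five: 12.8%; at least one of six: 13.5%;
- secondary significant and primary not: 13.5 − 4.6 = 8.9%;
- as a share of trials with a failed primary: 8.9/95.4 = 9.3%.

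| Scoring of women without IUA | At least one of five | At least one of six | Share of failed-primary trials with a significant secondary |
|---|---|---|---|
| 0 on extent and type | 8.7-15.4% (mostly 11-14%) | 10.6-16.5% (mostly 12-15%) | 5.8-11.9% (mostly 7-11%) |
| Left out (about 0.30 × 240 = 72 women scored) | 11.5-17.7% | about 16-22% | not simulated |

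The last column is conditional. The joint chance is about 0.95 times it: 0.95 × 5.8 = 5.5% to 0.95 × 11.9 = 11.3%. Either way it is roughly 6-12%. In the second row the six-test figure treats the primary as independent of the scores; on that footing the joint chance would be 0.95 × 11.5 = 10.9% to 0.95 × 17.7 = 16.8%.

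**4. Sensitivity to one undocumented choice.** In a separate run at 22.5% incidence and correlation 0.5, giving 10% of adhesion-free women hypomenorrhea moved the any-of-five rate from 10.6% to 12.8%, and the rate with a failed primary from 7.3% to 8.7%.

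**5. Effect of a gate.** If secondaries can be claimed only after a significant primary, the chance of any false claim under the global null equals the primary's own error (simulated 4.5-5.3%). Adding Holm over the five brings the chance of any secondary claim to about 1-2%. Holm without a gate gives about 2-3%.

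**The case against.** The best defence is that the confirmatory claim is already protected. There is one primary endpoint, one primary hypothesis and a sample size built on it; its error is untouched by what follows. The other endpoints are labelled secondary, and the plan does not say that formal claims on them are intended. This stands, and it limits the weight of the point. It does not remove it, because the plan is not merely silent: its significance rule reaches all analyses.

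Three stronger readings are tempting, and the documents do not support them.

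- A reader might infer that the plan breaches a 5% error rate it promises. It does not. The 0.05 is a per-test criterion, each test holds about that level, and no family-wise rate is stated.
- A reader might want one number, such as 13-14% for any secondary and 10% with a failed primary. Simulations assuming hypomenorrhea in 5-20% of adhesion-free women do give 12.8-14.2% and 9.0-11.1%. But the documents give no such rate, no item distributions or correlations, no stage test, and no scoring rule for women without IUA. Equally compatible assumptions give 9.5-10.8% and 6.3-7.6%. Only a range is defensible.
- A reader might call every significant secondary after a failed primary a false claim. That is true only if the gel does nothing. If it truly lowers incidence and women without IUA score 0, differences in extent, type, sum and stage are real even when the primary misses.

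**Conclusion.** The concern holds as a gap in the rules for secondary claims, not as an error in a stated figure. With no effect on any endpoint, the chance of at least one nominally significant secondary is roughly 9-15% under zero scoring and up to about 18% if only women with IUA are scored. The joint chance of a significant secondary and a non-significant primary is roughly 6-12% under zero scoring. Every scenario examined exceeds 5% for the secondaries as a set, so the direction is secure. The exact size is not, since it depends on the assumptions listed in the working. Primary inference is unaffected. This is a modest, inexpensive improvement.

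**What to change.** Add to the Statistical analysis Plan that a secondary endpoint may be called statistically significant only if the centre-adjusted CMH test on IUA incidence gives p ≤ 0.05, and that otherwise all five secondaries are reported descriptively, with estimates and 95% CIs.

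The gate alone does not control error among the secondaries once the primary has succeeded; a real effect on incidence could sit beside no effect on menstrual pattern, for example. If the sponsor wants formal claims on individual secondaries after a positive primary, one multiplicity procedure should be prespecified: a fixed order of the sponsor's choosing, or Holm. The documents dictate no particular order. Whichever is chosen, the SAP should also name the test for stage and say how women without IUA are scored, since the procedure cannot be applied without both.

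The cost is a short SAP paragraph, with no extra patients and no loss of power for the primary. The downside is that some nominal secondary p-values at or below 0.05 could no longer be called significant.
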